## 8.5. Multiple Comparisons and Multiplicity

The null hypothesis for the primary and secondary efficacy endpoints will be tested in a prespecified order using a closed testing procedure. This procedure will maintain the family-wise error rate at two-sided significance level of 0.0499 for all primary and secondary hypotheses tested in a confirmatory sense. The testing steps are described as follows:

- Step 1: The null hypothesis for the primary endpoint  $H_{01}$  is that there is no treatment difference in the change from baseline to Week 24 in ALSFRS-R total score between patients randomized to placebo and those randomized to reldesemtiv in the FAS. The hypothesis will be tested at the two-sided significance level of 0.0499. If this hypothesis is rejected, testing will proceed to Step 2; otherwise testing will stop.
- Step 2: The null hypotheses for the first secondary endpoint  $H_{02}$  is that the Mann-Whitney probability of a more favorable status in reldesemtiv or placebo group in the FAS is 0.5. The status is quantified by joint ranks based on the combined assessment of change in ALSFRS-R total score, time to onset of respiratory insufficiency, and survival time up to Week 24. The hypotheses will be tested at the two-sided significance level of 0.05. If this hypothesis is rejected, testing will proceed to Step 3; otherwise testing will stop.
- Step 3: The null hypotheses  $H_{03}$  is that there is no treatment difference in change from baseline to Week 24 in the percent predicted FVC between patients randomized to placebo and those randomized to reldesemtiv in the FAS. The hypotheses will be tested at the two-sided significance level of 0.05. If this hypothesis is rejected, testing will proceed to Step 4; otherwise testing will stop.
- Step 4: The null hypotheses  $H_{04}$  is that there is no treatment difference in change from baseline to Week 24 in the ALSAQ-40 total score between patients randomized to placebo and those randomized to reldesemtiv in the FAS. The hypotheses will be tested at the two-sided significance level of 0.05. If this hypothesis is rejected, testing will proceed to Step 5; otherwise testing will stop.
- Step 5: The null hypotheses  $H_{05}$  is that there is no treatment difference in change from baseline to Week 24 in handgrip strength (average of both hands) between patients randomized to placebo and those randomized to reldesemtiv in the FAS. The hypotheses will be tested at the two-sided significance level of 0.05. No further hypothesis testing will be carried out in this closed testing procedure.

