Twenty-four (24) weeks after at least one-third or more of the planned sample size is randomized, the second interim analysis will be triggered. The goal of the second interim analysis is to evaluate whether the proposed Phase 3 trial has adequate power to achieve a statistically significant effect on the primary endpoint in the final primary analysis, given the planned enrollment, or if continuing the trial is futile. At this interim analysis, the DMC will receive unblinded efficacy data from the independent, third-party biostatistical group supporting them and assess the effect of reldesemtiv on the primary endpoint. In terms of futility, the DMC may recommend stopping the trial if the conditional power (CP) is less than 0.10 for the primary endpoint.

If the CP of the primary endpoint is within a pre-specified promising zone from 0.40 to 0.90, the DMC may recommend increasing the sample size by 150 patients unless there is any safety concern or other concerns that preclude this recommendation. This interim analysis will spend a 2-sided alpha of 0.0001 for the primary endpoint and all individual secondary endpoints. The DMC is also expected to recommend stopping this trial due to superiority if a two-sided p-value is \leq alpha of 0.0001 for the primary endpoint as well as all individual secondary endpoints. Therefore, the significance level of 2-sided alpha of 0.0499 would be used for the final primary analysis for the primary endpoint to control familywise error rate at overall alpha of 0.05.

Statistical Methods:

Sample Size Justification:

With a 2:1 randomization ratio to reldesemtiv and placebo groups, respectively, a sample size of approximately 555 patients is required to achieve at least 90% power to detect at least a 1.8 point treatment difference between reldesemtiv and placebo in the change from baseline to Week 24 in ALSFRS-R total score. This calculation is based on a two-sample t-test with two-sided alpha at 0.05 level and a common standard deviation (SD) of 5.5 points, accounting for missing data and early treatment terminations.

Statistical Methods:

Unless specified otherwise, efficacy analyses will be performed on the full analysis set (FAS), which includes all randomized subjects who receive at least one dose of randomized study drug and have a baseline and at least one post-baseline efficacy assessments or have survival status recorded, by randomized treatment group.

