sample size, the CDL method could allow the final analysis to include all data before and after the interim look without inflating the type-1 error. This interim analysis will spend a very small 2-sided alpha of 0.0001 for the primary endpoint as well as all individual secondary endpoints. The DMC is also expected to recommend stopping this trial due to superiority if a two-sided p-value is  $\leq$  alpha of 0.0001 for the primary endpoint as well as all individual secondary endpoints. Therefore, the significance level of 2-sided alpha of 0.0499 would be used for the final analyses for the primary endpoint and all individual secondary endpoints to control familywise error rate at overall alpha of 0.05.

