## **6.4. Data Presentation Conventions**

The following conventions will be applied to data presentations:

- For continuous variables, mean and median values are formatted to one more decimal place than the measured value. Standard deviation values are formatted to two more decimal places than the measured value. Minimum and maximum values are presented with the same number of decimal places as the measured value.
- For categorical variables, the count and percentage of responses are presented in the form XX (XX.X%).
- Date variables are formatted as DDMMYYYY for presentation. Time is formatted from 0:00 to 23:59 as HH:MM for presentation.
- P-values, if applicable, will be presented to 4 decimal places. If the p-value is less than 0.0001 then it will be presented as <0.0001. If the rounded result is a value of 1.000, it will be displayed as >0.9999.
- Unless otherwise stated, any statistical tests performed following the second interim analysis (which will be performed at a significance level of 0.0001) will use 2-sided tests at the 0.0499 significance level.

The table and listing shells and table of contents as part of this SAP provide the expected layout and titles of the tables, listings and figures. Any changes to format, layout, titles, numbering, or any other minor deviation will not necessitate a revision to the SAP nor will it be considered a deviation from planned analyses. Only differences in the analysis methods or data handling will require such documentation. The appropriate listings supporting the tables will be included and are not specified in the individual sections throughout the document.

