## **8. EFFICACY**

### **8.1. General Considerations**

Unless otherwise specified, inferential statistical tests will be two-sided and will be performed at alpha levels of 0.05 to declare the significance of effects.

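### SAP 8.5 tests the four secondary endpoints at 0.05, although the plan's own alpha budget leaves 0.0499 for each of them

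*SAP*

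**What the plan says.** The alpha budget is set in SAP 5.1. On the second interim analysis it says: "This interim analysis will spend a very small 2-sided alpha of 0.0001 for the primary endpoint as well as all individual secondary endpoints". It concludes that "the significance level of 2-sided alpha of 0.0499 would be used for the final analyses for the primary endpoint and all individual secondary endpoints", with the stated aim "to control familywise error rate at overall alpha of 0.05". Protocol 9.5 gives the same rule for the primary and all secondary endpoints. The protocol synopsis is narrower and mentions 0.0499 only for the primary endpoint: "the significance level of 2-sided alpha of 0.0499 would be used for the final primary analysis for the primary endpoint". Protocol 9.4.1.1 gives the family-wise target as 5% and does not mention 0.0499.

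The hierarchy itself is in SAP 8.5, which opens with this claim: "This procedure will maintain the family-wise error rate at two-sided significance level of 0.0499 for all primary and secondary hypotheses". Step 1 (primary endpoint) is tested at 0.0499. Step 2 (joint-rank endpoint), Step 3 (percent predicted FVC), Step 4 (ALSAQ-40) and Step 5 (handgrip strength) each carry the sentence "The hypotheses will be tested at the two-sided significance level of 0.05".

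Two general rules in the SAP also bear on the level, and they disagree. Section 6.4 says that tests after the second interim, unless stated otherwise, "will use 2-sided tests at the 0.0499 significance level". Section 8.1 says that inferential efficacy tests, unless specified otherwise, "will be performed at alpha levels of 0.05 to declare the significance of effects".

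**The concern.** Section 8.5 contradicts its own opening claim, and it contradicts SAP 5.1 and protocol 9.5. The general rules do not settle the matter. Both 6.4 and 8.1 are defaults that give way to specific text, and they point in opposite directions. A programmer following the steps as listed would apply 0.05; one following 5.1 would apply 0.0499.

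The decision rule for four confirmatory endpoints is at stake. The protocol leaves the order of the secondary endpoints after the first to the SAP, so 8.5 is the only complete statement of the hierarchy. If a secondary p-value fell between 0.0499 and 0.05, one section would call it significant and another would not, and the choice would be made with the result in view. The first secondary endpoint could also gain weight: SAP 8.7.1 allows it to be considered as the primary endpoint before database lock if mortality is higher than expected, and 8.5 currently attaches 0.05 to it.

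**Working it through.** **Inputs**

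| Quantity | Value (two-sided) | Source |
|---|---|---|
| Overall family-wise rate | 0.05 | SAP 5.1; protocol 9.5 |
| Spent at second interim, primary and each secondary | 0.0001 | SAP 5.1; protocol 9.5 |
| Final level, primary and each secondary | 0.0499 | SAP 5.1; protocol 9.5 |
| Family-wise rate claimed for the hierarchy | 0.0499 | SAP 8.5 |
| Step 1 level | 0.0499 | SAP 8.5 |
| Steps 2 to 5 level | 0.05 | SAP 8.5 |
| Timing of second interim | 24 weeks after at least one-third of the planned sample is randomized | SAP 5.1 |

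**1. The plan's own figure.** The split is additive (Bonferroni): 0.05 − 0.0001 = 0.0499. The stated final level reproduces exactly.

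**2. Final-analysis error of the sequence.** In a fixed sequence, the worst case is that every null before the first true one is rejected with probability near 1. The family-wise error is then the level of the step at which that true null is tested.

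- First true null at Step 1: 0.0499.
- First true null at any of Steps 2 to 5: 0.05.

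The maximum is 0.05, which is 0.05 − 0.0499 = 0.0001 above the rate claimed in 8.5. This result does not depend on interim timing.

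**3. Total over both looks, upper bound.**

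- As written for a secondary endpoint: 0.0001 + 0.05 = 0.0501.
- With 0.0499 in Steps 2 to 5: 0.0001 + 0.0499 = 0.0500.

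**4. Total over both looks, allowing for correlation.** The final data contain the interim data, so the bound overstates the total. Take Z1 and Z2 as bivariate normal with correlation √t, where t is the information fraction at the interim. The total is P(|Z1| > c1 or |Z2| > c2), with c1 the critical value for 0.0001. The value of c2 is 1.95996 for 0.05 and 1.96082 for 0.0499. The documents fix t only as following from at least one-third of the sample, so the table shows a range as an assumption, with no sample size increase.

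| t (assumed) | Total, final test at 0.05 | Total, final test at 0.0499 | Final level giving a total of exactly 0.05 |
|---|---|---|---|
| 1/3 | 0.050031 | 0.049931 | 0.049969 |
| 1/2 | 0.050009 | 0.049909 | 0.049991 |
| 2/3 | 0.050001 | 0.049901 | 0.049999 |

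With the final test at 0.05 the total exceeds 0.05 at each of these fractions, by about 0.00003 at t = 1/3 and by almost nothing at t = 2/3. With 0.0499 it stays below 0.05 throughout.

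**5. Cost in power.** No effect sizes are given for the secondary endpoints, so the primary endpoint's design serves as a yardstick. With a difference of 1.8, SD 5.5, 2:1 allocation, 90% power and two-sided 0.05 (SAP 4.3.1), the placebo group needs 1.5 × 5.5² × (1.960 + 1.282)² / 1.8², which rounds up to 148. The total is 3 × 148 = 444. The planned 444 evaluable out of 555 implies 20% loss, and 444 / 0.80 = 555, so the plan's sample size reproduces. With 444 evaluable patients, power is 90.16% at 0.05 and 90.15% at 0.0499.

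**The case against.** The strongest reply is that this is an incomplete edit with almost no consequence. The opening sentence and Step 1 of 8.5 already carry 0.0499, primary inference is untouched, and 0.0501 is only a bound. The excess over the overall 0.05 is about 0.00003 at t = 1/3 and smaller later. The superiority rule can also be read as requiring p ≤ 0.0001 on the primary and all secondary endpoints together, which would usually make a false secondary rejection at the interim rarer still. Finally, the support elsewhere is uneven. SAP 6.4 is only a default that 8.5 overrides, SAP 8.1 covers efficacy tests generally, and the protocol synopsis and 9.4.1.1 do not set 0.0499 for secondary endpoints.

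Most of this stands as a statement about size. The rule for all secondary endpoints rests on SAP 5.1 and protocol 9.5, not on SAP 6.4 or the synopsis. The joint reading of the superiority rule does not change the worst case, because all other endpoints may have effects large enough to pass at the interim. The reply does not remove the contradiction: 8.5 claims 0.0499 for all primary and secondary hypotheses and then prescribes steps that do not deliver it.

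**Conclusion.** The concern holds. The level in Steps 2 to 5 of SAP 8.5 is wrong against SAP 5.1, protocol 9.5 and the opening claim of 8.5 itself. There are two targets, and they should be kept apart:

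- Against the 0.0499 claimed in 8.5, the worst-case final-analysis error is 0.05, an excess of 0.0001. This follows from the fixed sequence alone.
- Against the overall 0.05, the two-look excess is at most 0.0001. Under the bivariate normal calculation it is about 0.00003 at an assumed information fraction of 1/3, and less if the interim falls later.

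The practical effect is confined to a trial in which the primary and all earlier steps succeed and a secondary p-value lies between 0.0499 and 0.05. This is a small error in number, but it sits in the decision rule for four confirmatory endpoints and should be corrected before database lock.

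**What to change.** In SAP 8.5, replace 0.05 by 0.0499 in Steps 2, 3, 4 and 5. In SAP 8.1, replace the default of 0.05 by 0.0499 so that it agrees with 6.4. The 8.1 change is alignment; the correction itself lies in the four steps.

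This means changing five numbers in the SAP. No change to the design, sample size or analysis models is needed, and the loss of power is about 0.01 percentage points on the primary-endpoint yardstick (90.16% to 90.15%). The value follows directly from the budget already set in SAP 5.1 and protocol 9.5.

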## 8.6. Analysis of the Primary Efficacy Endpoint

### 8.6.1. Primary Efficacy Analysis

The primary efficacy endpoint of the trial is the change from baseline to Week 24 in ALSFRS-R total score. The estimand of the primary efficacy endpoint is the difference in the mean changes from baseline to Week 24 in ALSFRS-R total score between patients randomized to placebo and those randomized to reldesemtiv in the FAS.

The analysis for the primary efficacy endpoint will be conducted using a mixed model for repeated measures (MMRM) based on a restricted maximum likelihood method (SAS® PROC MIXED default). The model terms will include treatment group, baseline ALSFRS-R total score, visit, riluzole use at baseline, edaravone use at baseline as well as baseline-by-visit and treatment group-by-visit interactions. In addition, other baseline covariates identified by stepwise selection in a regression model will also be included in the model if they are key predictor variables for the change from baseline to Week 24 in ALSFRS-R total score. The regression model used to identify baseline covariates will include change from baseline to Week 24 in ALSFRS-R total score as response variable and pre-study disease progression rate, age and baseline percent predicted FVC as model terms. The stepwise selection process with significance at 0.25 level for a variable to be entered to the model and with significance at 0.1 level for a variable to remain in the model will be used. The best-fit model according to AIC will be selected. The evaluation will be performed based on the blinded data before the database lock. An unstructured variance-covariance matrix will be used for the model. Observed data collected up to Week 24 in the FAS will be included in the model.

Prior to applying the MMRM, multiple imputation with fifty invocations under the MAR paradigm will be performed to impute missing data (see [Section 8.6.1.1](#) for imputation method).

Least squares mean (LSM), LSM difference and the corresponding standard error, 95% CI and p-value will be presented. The components used to derive main estimator of the primary analysis are shown in [Table 4](#).

Sensitivity analyses will be conducted to support the robustness of conclusions based on the primary analysis results. See [Section 8.6.2](#) for sensitivity analyses.

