either active drug or placebo. The primary endpoint was rate of change in the ALSFRS-R; the decline was -1.24 points per month in the active arm and -1.66 points per month in the placebo arm ($p = 0.033$) (Paganoni 2020).

To date, there are no available treatments that slow the decline of skeletal muscle strength or slow the decline of respiratory function. This clinical protocol is a double-blind, randomized, dose-ranging, placebo-controlled trial to evaluate the efficacy, safety, and tolerability of reldesemtiv in patients with ALS.

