4. STUDY DESIGN

4.1. Overall Design

This is a Phase 3, double-blind, randomized, placebo-controlled trial of reldesemtiv in patients aged 18 to 80 with ALS.

The screening and qualification period for the trial will be no more than 21 days in duration. Approximately 555 eligible ALS patients will be randomized (2:1) to receive the following dose of reldesemtiv or placebo (stratified by riluzole use/non-use and edaravone use/non-use) for the first 24 weeks (double-blind, placebo-controlled period):

- 300 mg reldesemtiv twice a day for a 600 mg total daily dose (TDD)
- Placebo twice daily

At the end of the 24 week double-blind, placebo-controlled period, patients will transition to the active drug period, where all patients will receive the following dose of reldesemtiv for the next 24 weeks:

- 300 mg reldesemtiv twice a day for a 600 mg TDD for patients who were not down titrated during the 24 weeks of blinded dosing
- 150 mg reldesemtiv twice a day for a 300 mg TDD for patients who were down titrated for any reason during the 24 weeks of blinded dosing

For patients being seen in the morning of the Week 24 visit:

- Following the pre-dose PK, the last dose of double-blind study drug will be taken from the bottle received at the prior drug dispensation visit
- The patient will take their second dose of the day (which will be unblinded reldesemtiv) at home from the new bottle dispensed at the Week 24 visit approximately 8 hours after the first dose

If a patient is being seen in the afternoon for the Week 24 visit and taking their second dose of the day in the clinic:

- Following the pre-dose PK, the last dose of blinded study drug will be taken from the bottle received at the prior drug dispensation visit and they will take no further doses that day
- The following morning, the patient will start taking unblinded study drug (reldesemtiv) from the new bottle dispensed at Week 24.

For the entire 48 weeks of dosing, patients and sites shall remain blinded to the randomized treatment assignment the patients received during the first 24 weeks.

Study drug should be taken twice daily, morning and afternoon (at least 8 hours apart) and should be taken within a 2-hour period following food.

Study Visits:

There will be up to eight clinic visits and nine remote assessment visits (with most requiring an accompanying phone/video call) as follows:

- Screening: clinic visit/lab

- Day 1 (start of dosing): clinic visit/lab

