 110. Clinical laboratory findings within the normal range, or if outside the normal range, not deemed clinically significant by the Investigator, except as specifically indicated as laboratory exclusion in [Section 5.2](#).
 111. Able to swallow whole tablets at the time of screening
 112. Male patients, who have not had a vasectomy with medical assessment of surgical success, or a confirmed sperm count of zero, are eligible to participate if they agree to the following during the trial and for at least 10 weeks after the last dose of study drug:
 - a. Refrain from donating spermPlus when their female partner is of childbearing potential must either:
 - b. Be abstinent from heterosexual intercourse and agree to remain abstinentOR
Must agree to use a male condom AND have his female partner use a highly effective method of contraception during the study (as described in Appendix 3 [[Section 10.3](#)]), and also for at least 4 weeks after the last dose of study drug.
 113. A female patient is eligible to participate if she is not pregnant or breastfeeding, and at least one of the following conditions applies:
 - a. Is not a woman of childbearing potential (WOCBP; as described in Appendix 3 [[Section 10.3](#)])OR
Is a WOCBP and using a highly effective method of contraceptive during the study (as described in Appendix 3 [[Section 10.3](#)]) and also for at least 4 weeks after the last dose of study drug, and her male partner must agree to use a male condom during the trial and for at least 4 weeks after the last dose of study drug.
 - b. A WOCBP must have a negative pregnancy test (urine or serum as required by local regulations) within 3 days before the first dose of study drug.

Note: The investigator is responsible for review of medical history, menstrual history, and recent sexual activity to decrease the risk for inclusion of a woman with an early undetected pregnancy.

Contraceptive use by men or WOCBPs should be consistent with the guidance in Appendix 3 ([Section 10.3](#)) and local regulations regarding the methods of contraception for those participating in clinical studies.
114. Able to complete all screening procedures.
115. Must be either on the combination product (brand name only) of sodium phenylbutyrate and taurursodiol (also known as TUDCA, ursodoxicoltaurine or Tauroursodeoxycholic

acid) for ≥ 51 days prior to screening or not have taken it for at least 30 days prior to screening

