9.2. Sample Size Determination

With a 2:1 randomization ratio to reldesemtiv and placebo groups, respectively, a sample size of approximately 555 patients is required to achieve at least 90% power to detect a 1.8 point treatment difference between reldesemtiv and placebo in the change from baseline to Week 24 in ALSFRS-R total score. This calculation is based on a two-sample t-test with two-sided alpha at 0.05 level, a common standard deviation (SD) of 5.5 points, and accounting for missing data and early treatment termination.

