9.4.2. Primary Endpoint

The primary endpoint of the trial is the change from baseline to Week 24 in ALSFRS-R total score. The primary estimand is the difference in the mean changes from baseline to Week 24 in ALSFRS-R total score between patients randomized to placebo and those randomized to reldesemtiv during the placebo-controlled double-blind treatment in the full analysis set.

The primary analysis (main estimator) of the primary endpoint is as follows:

The primary endpoint will be analyzed using a MMRM based on a restricted maximum likelihood method (SAS® PROC MIXED default). The model terms will include treatment group, baseline ALSFRS-R total score, visit, riluzole use status at baseline, edaravone use status at baseline as well as baseline-by-visit and treatment group-by-visit interactions. An unstructured variance-covariance matrix will be used in the model. Additional important baseline covariates may be included to the primary analysis model if they are key predictor variables for the change from baseline to Week 24 in ALSFRS-R total score. Details of the selection procedure for the potential baseline covariates will be pre-specified in the SAP. The selection of the potential baseline covariates will be performed before the database lock.

Prior to applying the MMRM, missing data will be imputed using the multiple imputation procedure (Rubin 1987) for the primary analysis, and the estimates from each imputed dataset will be combined into one set of overall estimates using the SAS® PROC MIANALYZE procedure. The extent of missing data and the pattern of missing data reasons will be tabulated. Imputation details will be pre-specified in the SAP. Least square means (LSM), LSM difference and the corresponding standard errors, 95% CI and p-values will be presented.

Sensitivity analyses will be conducted to support the robustness of the primary analysis results. Using the ANCOVA model with the MAR-based multiple imputation for all missing ALSFRS-R assessments as the base model, the tipping point analyses will be conducted having the imputed values for the deaths successively worse only for the reldesemtiv treatment, while maintaining the MAR-based imputed values for the placebo treatment. Another sensitivity analysis will be to repeat the ANCOVA base model with missing ALSFRS-R assessments imputed as if the reldesemtiv patients were in the placebo arm. Other sensitivity analyses and the details will be included in the SAP.

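### Baseline use of the sodium phenylbutyrate/taurursodiol product is recorded and must be stable at entry, but the primary MMRM omits it and the stepwise list cannot admit it: a small, avoidable loss of precision, not a bias

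*SAP*

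**What the plan says.** **Entry and recording.** Protocol 5.1 (criterion 115) covers the product: "Must be either on the combination product (brand name only) of sodium phenylbutyrate and taurursodiol" for at least "51 days prior to screening or not have taken it for at least 30 days prior to screening". Criteria 108 and 109 set similar rules for riluzole and edaravone. Protocol 6.5 records use of all three, including use that ended before screening, and asks patients not to start or stop any of them after randomization.

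**Randomization.** Protocol 4.1 has allocation "stratified by riluzole use/non-use and edaravone use/non-use"; SAP 4.4 agrees. The combination product is not a stratum.

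**Primary model.** SAP 8.6.1 states: "The model terms will include treatment group, baseline ALSFRS-R total score, visit, riluzole use at baseline, edaravone use at baseline", with baseline-by-visit and treatment-by-visit interactions. Table 4 and the sample code in SAP 12.5 match.

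**Extra covariates.** Protocol 9.4.2 leaves room: "Additional important baseline covariates may be included to the primary analysis model if they are key predictor variables". It defers the procedure to the SAP, where the selection regression has only "pre-study disease progression rate, age and baseline percent predicted FVC as model terms". The product is not a candidate.

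**Elsewhere.** The product is not named in the imputation model (SAP 8.6.1.1 and 12.5) or among the subgroups (SAP 8.4.1). SAP 7.7.2 tabulates it by treatment received.

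**Cited effect.** For the product's own trial, Protocol 2.2.1 reports that "the decline was -1.24 points per month in the active arm and -1.66 points per month in the placebo arm" (p = 0.033).

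**The concern.** The protocol handles three background ALS therapies alike at entry and during follow-up, but the analysis adjusts for only two. No reason is given for leaving out the third, although the protocol itself reports an effect of that product on the scale used for the primary endpoint.

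A prognostic baseline variable that is neither stratified nor modelled can differ between arms by chance. Its contribution to outcome variance also stays in the residual. Adjusting for a value fixed before randomization cannot bias the treatment comparison, so the open question is whether the gain justifies the extra terms. At stake is a modest amount of precision in the primary estimate.

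**Working it through.** **Inputs from the documents.** Target difference 1.8 points, SD 5.5, two-sided alpha 0.05, power 90%, 2:1 allocation, about 555 randomized (Protocol 9.2); 444 evaluable (Protocol 1.1); declines of 1.24 and 1.66 points per month (Protocol 2.2.1).

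**Assumptions.** The share of users, p, is not given, so 5-30% is used. The cited effect is first carried over in full, then halved.

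**1. The plan's own sample size.** Placebo n = (1.960 + 1.282)² × 5.5² × (1 + 1/2) / 1.8² = 147.2, so 148. The total is 3 × 148 = 444, and 444 / 0.80 = 555. The stated figures reproduce, with power 90.2% at 444.

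**2. Cited effect at Week 24.** 1.66 − 1.24 = 0.42 points per month. Twenty-four weeks is 168 / 30.44 = 5.52 months, so e = 0.42 × 5.52 = 2.32 points.

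**3. Gain and exposure, full effect.** With 370 and 185 patients:
- share of variance explained: R² = p(1 − p) × 2.32² / 5.5²
- fall in the standard error: 1 − √(1 − R²)
- SD of the chance imbalance: √[p(1 − p)(1/370 + 1/185)]
- shift in the estimate at one SD: that SD × 2.32

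| p | R² | SE falls by | Imbalance SD (percentage points) | Shift (points) |
|---|---|---|---|---|
| 5% | 0.8% | 0.4% | 2.0 | 0.05 |
| 10% | 1.6% | 0.8% | 2.7 | 0.06 |
| 20% | 2.8% | 1.4% | 3.6 | 0.08 |
| 30% | 3.7% | 1.9% | 4.1 | 0.10 |

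The standard error of the treatment difference is 5.5 × √(1/370 + 1/185) = 0.50, so the shift is roughly 10-20% of one standard error. With 444 evaluable patients, power rises from 90.2% to 90.4% at 5% use and to 91.2% at 30%.

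**4. Half the effect (1.16 points).** R² falls fourfold, to 0.2-0.9%. The shift halves, to about 0.02-0.05 points. Power is 90.2-90.4%.

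**5. Would a single yes/no term be enough?** A difference in slope grows with time; a main effect is one constant across Weeks 4, 8, 12, 16, 20 and 24. The simple average of a linear effect over those visits is 2.32 × (4 + 8 + 12 + 16 + 20 + 24) / (6 × 24) = 1.35 points. With an unstructured covariance, the fit gives more weight to the less variable early visits. If change scores followed a Brownian pattern, the fitted constant would be the Week 4 effect alone: 2.32 × 4/24 = 0.39 points, or 17% of the Week 24 effect. Other covariances that were tried also gave small shares, about 8-23% in one set. These covariances are assumptions, but a main effect alone would leave most of a Week 24 imbalance uncorrected.

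**6. Size of the imputation models.** Imputation runs separately by arm over six visits, so one added covariate means up to 2 × 6 = 12 coefficients. At 5% use the placebo arm has about 0.05 × 185 = 9 users before dropout.

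**The case against.** The strongest defence is that nothing here is an error. The two background-therapy terms are the two stratification factors, and modelling those is a recognised rule. Leaving out an unstratified covariate neither biases the randomized comparison nor inflates type 1 error, and the standard error already allows for chance imbalance. All of this stands.

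The cited effect is also weak support for a firm gain. It is a randomized contrast from another trial, with 137 participants. Here the users are self-selected and have taken the product for at least 51 days. With p = 0.033, a normal approximation gives z = 2.13 and a standard error of 0.42 / 2.13 = 0.197 per month. The 95% limits over 24 weeks are then about 0.2 to 4.4 points, and at the lower limit adjustment gains nothing. Protocol 2.2.1 reports approval only in Canada and the US, while sites also lie in Europe and Australia, so users may be few and concentrated by region. This too stands, and it is why the figures are conditional. It does not remove the case for adjusting: a prognostic covariate need not be causal.

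Because 2.32 exceeds the 1.8-point target, a reader might infer that the omission could distort the trial's result. The documents do not support that. The comparison would matter only if the arms differed greatly in use; even a 10-percentage-point imbalance moves the estimate by 0.10 × 2.32 = 0.23 points, and SAP 7.7.2 would show such an imbalance.

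A reader might also extend the point to the secondary MMRMs. The documents give no evidence for that: the cited effect concerns ALSFRS-R alone, and Protocol 2.2.1 says that no available treatment slows the loss of muscle strength or respiratory function.

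**Conclusion.** The point holds as a low-cost refinement. The product is recorded, must be stable at entry and is excluded from the primary model by a closed list of candidates. The consequence is a small loss of precision and exposure to chance imbalance, with no systematic bias.

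The gain of 0.8-3.7% of variance, and the one-SD shift of 0.05-0.10 points against a standard error of 0.50, rest on two assumptions that the documents cannot confirm: the cited effect carries over in full, and 5-30% of patients are users. They are also measured against the planning SD of 5.5, not the residual after the other covariates. If either the effect or the use is smaller, the gain approaches zero. The primary analysis is valid without the change.

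**What to change.** Before unblinding, amend SAP 8.6.1, Table 4 and the sample code so that the primary MMRM includes baseline use of the combination product (yes/no) and its interaction with visit. A main effect alone is not enough, for the reason in step 5 of the working.

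Add the same variable to the imputation model in SAP 8.6.1.1 only if there are enough users per arm to estimate it. The blinded pooled count and the 2:1 ratio give the expected number per arm, so the minimum can be fixed in advance without unblinding.

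Leave the secondary MMRMs as they are on this point.

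Cost: about six parameters in the primary model (one per post-baseline visit), and up to 12 coefficients across the by-arm imputation models, which would be poorly estimated if use is rare. No new data collection is needed.
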